4.5.3 Blinding and Conditions for Unblinding

The injections will be prepared by an unblinded site pharmacist or otherwise qualified personnel who is not involved in any subject assessments and who will not discuss randomizations with blinded study staff. The subjects, study personnel who perform study injections and assessments, data entry personnel at the sites, and laboratory personnel performing immunologic assays will be blinded to the treatment assignment of all injections. Subject study injection assignments will be provided to the site Principal Investigator (PI) at completion of the study for communication to the study participants. The DSMB may receive data in aggregate and presented by treatment group during the study, but without the treatment group identified. The DSMB may be unblinded to individual study treatment assignments, as needed, to adequately assess safety issues.

If necessary, the site PI (or designee) and Protocol Chair may agree that management of an AE requires emergency unblinding of an individual subject's assignment following the first injection. This will be documented as a protocol deviation and the Protocol Statistician, the site IRB, and the DSMB will be notified that an early unblinding has occurred and provided with a statement explaining the medical necessity for the early unblinding. For further details on unblinding in the study, consult the Study Blinding Plan.

4.6 Safety and Immunogenicity Variables and Chikungunya Infection Incidence

4.6.1 Safety

Solicited AEs will be recorded in the study database with data collection for 7 days after both the first and second study injections. All unsolicited AEs will be recorded separately in the database from receipt of first study injection through 4 weeks after the last study injection administered. At subsequent follow-up visits, only serious adverse events (SAEs) and new chronic medical conditions will be recorded through the last study visit.

4.6.2 Immunogenicity

The principle immunogenicity endpoint is measured 4 weeks post second injection (Week 8) by neutralization assay.

4.6.3 Chikungunya Infection Incidence

The primary variable for this analysis is PCR-confirmed CHIKV illness. Reports of clinical illness with or without PCR confirmation will also be provided. Throughout the study if a subject reports signs and symptoms of CHIKV infection, blood samples should be collected for diagnostic testing by virus detection (e.g., PCR) by the Primary Diagnostic Laboratory (PDL). This may occur during a scheduled study visit or unscheduled visits may be conducted to complete the testing needed. CHIKV cases will be recorded through the last study visit. Laboratory confirmed cases of CHIKV will be recorded on a CHIKV endpoints form rather than on an AE form without an attribution assessment.

5 SAMPLE SIZE CONSIDERATIONS

The study design is to enroll 400 healthy adult participants ages 18 to 60 that reside in CHIKV endemic areas. Randomization will equally allocate subjects to vaccine or placebo schedules with electronic stratification by ages 18-40 and 41-60 years. The enrollment plan does not include provision for replacing subjects with incomplete injections or visit schedules.

Enrollments may occur rapidly at more than one site. The sample size for this study was not selected to test a formal null hypothesis, rather it reflects the number of vaccine doses that are available for the study and the desire to gain maximal information for the possible conduct of Phase 3 follow on trials. There are not good data to estimate the loss to follow-up rate for this study. The power calculations assume a 10% loss in both groups for the primary and secondary endpoints.

5.1 Power Calculations for Evaluation of Safety

The goal of the safety evaluation for this study is to identify safety concerns associated with injections of the investigational vaccine. Two sample size calculations for safety are expressed in terms of two approaches, within group and comparing two groups.

1. The ability to detect safety or reactogenicity events within each injection group:

The ability of the study to identify safety events may be expressed in terms of the probability of observing one or more event of interest (e.g., AEs) assuming a range of “true” but unknown event rates. The power to observe one or more event in a single group of 180 subjects is 83.62% when the true rate is 1.0% and 97.37% when the true rate is 2.0% (Table).

Table 2: Probability of Observing One or More Safety Events within a Group (n=180)

True Event Rate	Pr (1 or more events)
0.01%	1.78%
0.10%	16.48%
0.33%	45.17%
0.50%	59.43%
1.00%	83.62%
2.00%	97.37%

2. The minimum detectable difference in safety event (e.g., AEs) rates for comparing two injection groups using Fisher’s exact test:

Safety event rates may vary considerably with the type of event considered therefore a wide range of possible rates is considered for comparison by vaccine group (Table).

Table 3: Minimum Detectable Differences in Event Rates for Power = 80% or 90% Assuming Type I Two-Tail Error Rate of 5% (n=180 per Group)

Power	Assumed Event Rate in Group 1 (n=180)	Minimum Detectable Event Rate Group 2 (n=180)	Difference in Rates
80%	0.1%	5.5%	5.4%
	1.0%	7.5%	6.5%
	5.0%	14.2%	9.2%
	25%	39.3%	14.3%
90%	0.1%	6.9%	6.8%
	1.0%	8.9%	7.9%
	5.0%	16.0%	11.0%
	25%	41.6%	16.6%

5.2 Power Calculations for Evaluation of Immune Responses

A secondary objective is to evaluate the humoral immunogenicity of VRC-CHKVLP059-00-VP by neutralization assay at 4 weeks after the second 20 mcg dose (Week 8). Vaccine specific neutralization antibodies are not anticipated in the non-vaccinated group. Therefore, direct comparison between the active and placebo group is of minimal value in assessing sample size. Preliminary Phase 1 neutralization data suggest that neutralization results at the visit with peak response are log-normally distributed with a mean and standard deviation on the log-scale of 7.41 and 0.67 respectively. This standard deviation is rounded up to 0.70 and two more conservative options of 1.0 and 1.5 result in 95% confidence intervals (CI) for geometric mean titers (GMT) (Table).

Table 4: 95% CI for GMT Neutralization among Vaccinees at Time of Peak Response (n=180 per Group)

Assume Standard Deviation on Log Scale	95% CI for GMT Neutralization Among Vaccinees (n=180) at Time of Peak Response
0.70	(1490.7, 1831.7)
1.0	(1426.6, 1914.1)
1.5	(1324.8, 2061.1)

The study is not designed to compare two groups defined by baseline covariates such as gender or age strata. However, the following table is included to provide a sense of the power available for such comparisons. The simple case of two groups (e.g., male and female), assuming equal participation (i.e., 90 subjects for each gender-vaccine group), is given in Table for comparing response rates.

Table 5: Detectable Geometric Mean Ratio between Two Groups for Power = 80% or 90% Assuming Type I Two-Tail Error Rate of 5% (n=90 per Group)

Power	Standard Deviation on Log Scale	Detectable Geometric Mean Ratio (n=90 per group)
80%	0.7	1.34
	1.0	1.52
	1.5	1.88
90%	0.7	1.40
	1.0	1.63
	1.5	2.08

6 GENERAL STATISTICAL CONSIDERATIONS

6.1 General Principles

All continuous variables will be summarized using the following descriptive statistics: n (non-missing sample size), mean, standard deviation, median, maximum and minimum. The frequency and percentages (based on the non-missing sample size) of observed levels will be reported for all categorical measures. In general, all data will be listed, sorted by site, treatment and subject, and when appropriate by visit number within subject. All summary tables will be structured with a column for each treatment in the order (Experimental, Control) and will be annotated with the total population size relevant to that table/treatment, including any missing observations.

Summary statistics for discrete data will include estimates and confidence intervals for binomial data; contingency tables, along with summary analyses such as tests of independence. Two-by-two tables may also include summaries of risk differences or risk ratios as is appropriate along with their confidence intervals.

Tabulations will be used extensively to summarize the data and will include summary statistics. For continuous data, tables will include measures of central tendency such as the mean, geometric mean, or median, and measures of dispersion such as the standard deviation or inter-quartile range. Tables of discrete data will include proportions and their confidence intervals.

Unless noted, statistical analyses will use standard methods as described below.

6.2 Timing of Analyses

This study is addressing an emerging and potentially expanding epidemic of Chikungunya. Therefore, at any time during the study an **unplanned** analysis may be required. There is no intention to use such an analysis to modify the study design. The extent of unblinding (e.g., group versus individual level and parameters examined) and the distribution of results will be limited to the maximal extent compatible with necessary use of the results. For example, site investigators will not receive interim results without an explicit request from the PI. Absent any possible safety concerns in a blinded review of the results, unblinded analyses will focus on immune responses and CHIKV incidence. The PSRT may also request an unblinding of the safety data at any time if, in their opinion, data internal or external to the trial requires such a review.

If any interim analyses are conducted, a separate analysis plan will be established to further describe the nature of the analyses and presentation of data. While these interim results may be used for design of future trials they will not be used to modify the design of this protocol.

Final analyses and the production of a CSR will occur when all subjects have completed their follow-up or have otherwise been prematurely censored, their data is cleaned within the limitations of practical follow-up and the database is locked.

6.3 Analysis Populations

The **Safety** population will include all enrolled subjects, summarized according to the actual vaccination received.

The **Per Protocol (PP)** analyses will include all subjects receiving two injections within window as assigned by the randomization schedule, and not experiencing any other major protocol deviations prior to their week 8 visit. Major protocol deviations include ineligibility, product administration deviations, and primary endpoint missing data. The subjects will be analyzed based on product actually received, regardless of randomization assignment. If subjects receive study vaccine for one visit and placebo for the other, then they will be included in the PP population until they receive the second injection or are otherwise removed from the PP population. The PP analyses will also include subjects determined to be CHIKV infected prior to the receipt of their scheduled second injection and not experiencing any other major protocol deviations prior to their state of infection. Subjects will be censored from the immunogenicity analysis following PCR-confirmed CHIKV infection. Immunogenicity and infection rates will both be examined for the PP population.

The **Intent-to-treat (ITT)** population will include all enrolled subjects, analyzed according to the randomized treatment. The ITT population will be used to analyze immunogenicity and infection rates.

The **Modified intent-to-treat (mITT)** analyses will include all enrolled subjects that received at least one product administration with non-missing immunogenicity data at their Week 8 visit, analyzed according to the study product(s) received. This definition will exclude subjects with protocol deviations related to possible dosing errors. The mITT population will only be used for immunogenicity analyses.

Subjects excluded from Immunogenicity (or CHIKV Incidence) analyses are listed in Appendix III, **Listing 16.2.3**.

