4.2.6. Study Visits and Sample Collection

The schedule of visits, permitted windows for completing the visits, and evaluations performed at each visit is shown in the table in [Appendix III](#). After Day 0, deviations from the visit windows in completing study visits are discouraged and will be recorded as protocol deviations, but are permitted, at the discretion of the PI (or designee).

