6.4. Statistical Analysis

Study enrollment is defined in this protocol as being randomized and receiving the first study injection. All enrolled subjects will receive at least one injection and therefore will provide some safety data. The safety population will include all enrolled subjects, summarized according to the actual vaccination received.

The Intent-to-treat (ITT) population will include all enrolled subjects, analyzed according to the randomized vaccine. The Per Protocol (PP) analyses will include all subjects receiving two vaccinations within window as assigned by the randomization schedule, and not experiencing any other major protocol deviations prior to their Week 8 visit. The PP analyses will also include subjects determined to be CHIKV infected prior to the receipt of their scheduled second vaccination and not experiencing any other major protocol deviations prior to their date of infection. Subjects will be censored from the immunogenicity analysis following CHIKV infection. The Modified intent-to-treat (mITT) analyses will include all enrolled subjects with evaluable immunogenicity data at their week 8 visit, without exclusions for protocol deviations or censoring for CHIKV infection. Additional cohorts may be defined in the Statistical Analysis Plan (SAP).

No formal multiple comparison adjustments will be employed. Imputation of missing values is not planned. They may be implemented for secondary or tertiary outcomes if supported by the data and if sufficient consequence to justify their inclusion. Analysis variables include baseline, safety, reactogenicity, and immunogenicity variables for primary and secondary objective analyses, respectively. Exploratory analyses will estimate CHIKV infection rates, and evaluate additional immunogenicity assays.

In general, descriptive statistics by vaccine group will be tabulated for all variables of interest, stratified by age as is appropriate. This will include point estimates (mean, geometric mean, median or proportions) and their respective 95% CI or percentile spread. Formal comparisons will use standard methods, contingency tables for categorical variables, t-tests or non-parametric analogs for comparing means or geometric means, logistic regression and analysis of covariance for model discrete and continuous variables respectively.

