APPENDIX III: SCHEDULE OF EVALUATIONS

VRC 704 Schedule of Evaluations														
Visit	01	02	02A	03	03A	04	05	06	07	08	09	10	11	12
Week of Study	-8 to 0	W0	W1	W4	W5	W8	W16	W24	W32	W40	W48	W56	W64	W72
Day of Study	-56 to 0	D0 ¹	D7	D28	D35	D56	D112	D168	D224	D280	D336	D392	D448	D504
Clinical Evaluations														
² Informed Consent, AoU	X													
³ Targeted physical exam	X	[X]		[X]		[X]								
Targeted medical history; vital signs	X	X	X	X	X	X	X	X	X	X	X	X	X	X
⁴ Study Injections		X		X ⁵										
Begin 7-Day Diary Card		X		X										
Phone contact; clinic visit if indicated			X		X									
Counseling on pregnancy prevention		X		X		X								
CBC, differential, platelets				3	3	3								
⁶ Pregnancy test: urine (or serum)		X	X	X			X							
ALT		4	4	4		4								
HIV ⁷ , creatinine		4												
Research Immunology														
Antibody assays and serum		40		40		40	40	40	40	40	40	40	40	40
⁹ Serum for diagnostic testing				[X]		[X]								
⁹ Plasma for diagnostic testing				[X]		[X]								
¹⁰ PBMC and plasma		[40]		[40]										[40]
Daily Volume (mL)	27	87	-	87	-	47	40	80						
Cumulative Volume estimate (mL)	27	114	-	201	-	248	288	328	368	408	448	488	528	608

¹ Day 0=day of enrollment and (blinded) CHIKV VLP vaccine or PBS injection. Day 0 evaluations prior to first injection are the baseline for assessing adverse events subsequently. Schedule Visits 02A through 04 with respect to the last prior injection day and subsequent visits with respect to Day 0. The visit windows are: Visits 02A and 03A (+3 days); Visit 03 (+14 days); Visit 04 (±7 days); Visits 05 through 12 (±21 days).

² Screening evaluations may be repeated or completed over more than one visit, if needed. Screening research blood draw and consent obtained more than 56 days prior to enrollment are not required to be repeated.

³ Screening physical exam is targeted to eligibility and includes height/weight; the [X] at other visits indicates targeted exam only if needed based on interim history.

⁴ Safety and research blood and vital signs must be collected before study injections are administered. Complete BP, pulse and injection site assessment at 15 minutes or later after study injection before subject leaves the clinic.

⁵ The preferred window for the second injection is +14 days. The injection may occur outside the preferred window with approval by the Protocol Chair.

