3.2.2 Secondary Endpoints

Immunogenicity

- Humoral immune response as measured by neutralization antibody (NAb) assay at baseline (Day 0) and at 4 weeks after second injection (Week 8).

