7.2 Protocol Deviations

A summary of subject-specific protocol deviations will be presented by the reason for the deviation, the deviation category, and treatment group for all subjects (**Table 14.1.5**). Deviations that are considered major in the categories of ineligibility, product administration, and primary endpoint missing data will be reviewed for possible subject exclusion from the per protocol population. All subject-specific protocol deviations and non-subject-specific protocol deviations will be included in Appendix III as data listings (**Listings 16.2.2.1 and 16.2.2.2, respectively**).

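### The per-protocol set controls when the injections are given but not when the Week 8 NAb sample is drawn; the existing Visit 04 window should be carried into PP immunogenicity

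*Combined protocol and SAP*

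**What the plan says.** - **Endpoint.** SAP 3.2.2 places the NAb measurement at baseline and "at 4 weeks after second injection (Week 8"). SAP 9 treats the second of these as the principal immunogenicity time point.
- **Visit window.** Protocol Appendix III, footnote 1, gives "Visits 02A and 03A (+3 days); Visit 03 (+14 days); Visit 04 (±7 days"), with Visit 04 counted from the last prior injection. Letter of Amendment #2 leaves that reference point unchanged for Visit 04 and adds no analysis window.
- **Departures.** Under Protocol 4.2.6, "deviations from the visit windows in completing study visits are discouraged and will be recorded as protocol deviations, but are permitted" at the investigator's discretion.
- **PP definition.** SAP 6.3 admits "all subjects receiving two injections within window as assigned by the randomization schedule, and not experiencing any other major protocol deviations prior to their week" (the cut-off being Visit 04). Protocol 6.4 has the same structure.
- **Major deviations.** SAP 6.3: "Major protocol deviations include ineligibility, product administration deviations, and primary endpoint missing data". SAP 7.2: "Deviations that are considered major in the categories of ineligibility, product administration, and primary endpoint missing data will be reviewed for possible subject exclusion" from PP.
- **Shells.** Table 14.1.5 gives departures from the follow-up visit schedule their own row, separate from product administration. The PP exclusion reasons in Table 14.1.2 cover an injection out of window, a major deviation before the Week 8 visit and an error in the second injection. For immunogenicity, PCR-confirmed infection is added. None concerns the date of the sample.
- **Other sets.** mITT asks only for a non-missing Week 8 result. SAP 9 sets no sampling window for any set.
- **Dates.** SAP 9 promises planned and actual collection dates in Listing 16.2.6. The shell has a collection date but no planned date and no dose 2 date.

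**The concern.** A PP immunogenicity set is meant to show the response to the regimen as given and measured at the intended time. Here the first half is controlled and the second is not. The protocol sets a sampling window and then permits visits outside it, and no analysis set takes the window up. Protocol 6.4.3 itself expects titers to decay. Followed as written, the PP rule lets the Week 8 GMT and the ratio to baseline mix on-time titers with earlier and later ones. Because results are also shown by site, uneven visit timing could look like a site difference. No error rate is at stake: the endpoint is secondary, the analysis is descriptive, and there is no formal hypothesis.

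**Working it through.** **1. The plan's own precision figure.** Inputs: 200 per group and 10% loss (SAP 5); log-scale mean 7.41 and SD 0.70 (SAP 5.2).

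- n = 200 × 0.90 = 180
- CI = exp(7.41 ± t(0.975, 179) × 0.70/√180) = (1490.8, 1831.6), against (1490.7, 1831.7) in SAP Table 4. It reproduces within rounding.
- GMT = exp(7.41) = 1652.4, so the CI reaches a factor of 1831.6/1652.4 = 1.108 either side, or about 11%.

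**2. The operational window.** 28 ± 7 gives 21–35 days after dose 2. With dose 2 on day 28 to 42, that is study day 28 + 21 = 49 to 42 + 35 = 77. The PP text has no matching bound.

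**3. A sample drawn 60 days after dose 2, put through the PP rule.**

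| Test | Result |
|---|---|
| Two injections in window | met |
| Ineligibility | none |
| Product administration deviation | none |
| Endpoint data missing | no, a titer exists |
| Recorded deviation | follow-up visit schedule, not one of the three categories in SAP 7.2 |
| Table 14.1.2 reason | only the general major-deviation row, if someone judges the lateness major |

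By default the titer stays in PP as Week 8.

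**4. Possible size.** The documents give neither the share of off-window samples nor a decay rate, so both are assumed. If a share f is d days late and the half-life is h days, the GMT is multiplied by 2^(−f·d/h). With d = 28:

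| Share late | h = 60 | h = 30 |
|---|---|---|
| 10% | 2^(−2.8/60) = 0.968 (−3.2%) | 2^(−2.8/30) = 0.937 (−6.3%) |
| 20% | 2^(−5.6/60) = 0.937 (−6.3%) | 2^(−5.6/30) = 0.879 (−12.1%) |

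Doubling the longer half-life to 120 days gives −1.6% (10% late) and −3.2% (20% late). Only the 20%, 30-day cell exceeds the CI half-width. Early samples are not quantified, because the documents give no rate of rise.

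**5. Response status.** The SAP 3.3 cut-off is 30. At the faster decay, a typical late titer is 1652.4 × 2^(−28/30) = 1652.4 × 0.524 = 865. On the log scale, (ln 865 − ln 30)/0.70 = (6.76 − 3.40)/0.70 = 4.8 SD above the cut-off. With the SAP's widest SD of 1.5 it is still 3.36/1.5 = 2.2 SD above.

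**6. Cost of a timing rule in PP** (SD 0.70, assumed exclusions from 180):

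| Excluded | n | 95% CI |
|---|---|---|
| none | 180 | 1490.8–1831.6 |
| 5% | 171 | 1486.7–1836.6 |
| 10% | 162 | 1482.4–1842.0 |
| 20% | 144 | 1472.5–1854.4 |

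**The case against.** Four stronger readings are tempting, and the documents do not support them.

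- **That no planned output would show off-window sampling.** Table 14.1.5 counts follow-up schedule deviations by group, and Listing 16.2.2.1 gives each deviation with its date. Listing 16.2.6 gives collection dates, and Listings 16.3.2 and 16.3.3 give the dose 2 date. Days since dose 2 could be worked out by joining listings. But Table 14.1.5 does not isolate Week 8, and no immunogenicity result uses the information.
- **That the PP wording cannot reach a late Week 8 visit.** The list of major deviations is introduced by a verb that can be read as open-ended. A window that closes on day 35 has also already been missed before a day-60 visit takes place. So there is room to call the sample a major deviation. SAP 7.2 and Table 14.1.2 point the other way, and such a decision would not be pre-specified.
- **That a missing diary card could remove someone from PP immunogenicity, because SAP 3.2.1 lists the primary endpoints as safety.** The note to Figure 14.2.1 calls neutralization the primary immunogenicity endpoint, and PP is used only for immunogenicity and infection rates. The natural meaning of the third category is a missing Week 8 NAb result, and SAP 7.2 provides only for review, not automatic removal. The wording should be tidied, no more.
- **That the secondary endpoint as a whole is compromised.** SAP 6.3 uses ITT, mITT and PP for immunogenicity and names none as principal. The gap affects what PP is supposed to add.

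The assumed decay may also be too fast. A constant 30-day half-life would take 1652.4 to 1652.4 × 2^(−168/30) ≈ 34 in 24 weeks, close to the cut-off of 30. That sits poorly with the durable Phase 1 antibodies described in Protocol 1.4. Nothing in the documents suggests that 10–20% of samples would be four weeks late. Both points stand and limit the size of the concern, but neither supplies the missing rule.

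**Conclusion.** The concern holds as a low-cost improvement. SAP 6.3, SAP 7.2 and Table 14.1.2 control the injection window but do not carry the protocol's Visit 04 window into the PP immunogenicity set. A NAb sample outside 21–35 days after dose 2 can therefore be analysed in PP as Week 8. The true effect cannot be computed from the documents. The 3–12% fall in GMT rests on assumed half-lives of 30–60 days and on 10–20% of samples being 28 days late. It shrinks with slower decay and passes the roughly 11% CI half-width only at the extreme of both assumptions. The shift would be systematic rather than random, but it would rarely alter a subject's positive response status and bears on no formal test.

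**What to change.** - In SAP 6.3 and 7.2, for PP immunogenicity only and not PP infection rates, require the Week 8 NAb sample to fall within the existing Visit 04 window after dose 2.
- Add a row to Table 14.1.2: *Week 8 sample out of window*. Listing 16.2.3 then follows, since its shell must agree with that table.
- Keep these subjects in ITT and mITT, so that results including off-window samples are still reported.
- In Listing 16.2.6, add the planned collection date that SAP 9 already promises, and days since dose 2.
- As a wording clarification, replace the missing-primary-endpoint category with *missing Week 8 NAb result*.

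The cost is SAP wording, one table row and one variable derived from dates already collected. The downside is a slightly smaller PP set: with 10% excluded, the CI at SD 0.70 widens from 1490.8–1831.6 to 1482.4–1842.0. The rule should be fixed before database lock.
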